4. **Potential for reflex syncopal event:** Syncope is defined as a momentary loss of awareness and postural tone. It typically has a rapid onset, short duration, and spontaneous recovery. Although syncopal episodes are very rare with TMS (less than 1%), they typically occur during the motor

- threshold procedure before the rTMS treatment has begun. Individuals that are sleep deprived and have low or unstable blood pressure are at greater risk.
5. Interaction with electrical or metal implants: Electrically, magnetically or mechanically activated implants (such as cardiac pacemakers), as well as clips on blood vessels in the brain may be affected by rTMS (as well as MRI) and cause pain or abnormal signal propagation. Although the pain has not reported to be significant protocol-approved research study members will conduct a thorough TMS safety questionnaire. This questionnaire will be checked and updated throughout the course of the study. Individuals that have these implants and devices or suspect that they may have pieces of metal in their eyes, head, or body (e.g. bullets, shrapnel, and fragments from metallurgy) will be excluded from the study in order to minimize any discomfort and abnormal signal propagation.

Risks regarding Randomization and Alcohol Related Cues:

Given that participants will be exposed to alcoholic beverages, there may be an added risk of induced cravings. However, it should be noted that the alcohol cues that participants will be exposed to are not as powerful as the daily cues that participant's encounter in their normal living environment. In addition, participants that will be randomized receive the placebo treatment may prove to be less effective than real study treatment(s) or other available treatments.

Risks regarding Confidentiality:

Despite efforts to maintain subjects' anonymity and confidentiality, there is always some minimal risk of people other than the study investigators gaining access to your health information. Every effort will be made to ensure that your health information will be collected and stored in a manner that ensures the highest level of protection of confidentiality.

Protocol for participants expressing suicidal ideation: All study team members performing the Becks Depression Inventory will have received online training from the Suicide Prevention Resource Center (<https://training.sprc.org>). Completion documentation will be saved on the laboratory drive. In the event that a participant expresses a desire to kill themselves (selects answer #2 or #3 on question #9 of the Becks Depression Inventory), the trained study team member will ask them about the level of detail of their thoughts. If the participant has a suicide plan to kill himself/herself, the study staff will recommend he/she speaks with the suicide hotline and initiate contact with the suicide prevention hotline (Cardinal Innovations at [name]) while the individual is in their presence. If the participant refuses to talk to the hotline and leaves, the study staff will call 911. A member of the study team will initiate contact with a local, licensed clinician while the individual is in their presence. If the licensed clinician deems necessary, they will dispatch a mobile crisis unit to the location to further assess and transport the participant to the hospital for a full mental health assessment and involuntary 72-hour hold, if needed. The study staff member will also contact the PI via phone, email, or text as soon as possible to inform them of the situation.

Subject Recruitment Methods

Participants will be identified and recruited through members of the study team and the trained counselors and staff of the Wake Forest Department of Surgery's inpatient trauma unit in an appropriate manner with particular sensitivity surrounding their admission and PHI. If the potential participant is interest, they will screened and consented during their admission, serving as Visit 1. Additionally, heavy alcohol users with a history of risky drinking behavior will be recruited through the resources of the Wake Forest Trauma Unit Registry and community advertising. The MRI scans and TMS sessions during Visit 2 will both be performed at the MRI center on the WFUBMC main hospital campus. The study team will try to coordinate study visits on the same day as outpatient clinic follow up in Janeway Tower from their recent inpatient admission, as to make it easier on the participant. A meal voucher of \$10 will be provided for the participant to eat in the hospital cafeteria, should they so choose.

Additionally, a chart review will be conducted for research purposes. Potentially eligible patients will be identified. The potentially eligible patients in the PIs practice will be informed about the study as the PI feels is appropriate. Then potential patients who have agreed to be contacted for future research by logging their WFU Research Permissions preferences in MyChart will be contacted by phone and invited to participate. All other patients will be contacted through their providers to be informed of the study if the provider feels it is appropriate.

Informed consent will be reviewed with the potential participant by a member of the key personnel on this visit. The consent will be signed by the participant as well as one of the Key Personnel on the proposal. A copy of the consent will be given to the subject and the original placed in the research record. The consent and HIPAA process will be done in [name] research laboratory and facility.

Informed Consent

Individuals that have previously consented to be contacted about future research studies will be contacted and phone screened to determine preliminary eligibility. They will be scheduled for their screening visit, which will take place in a private, quiet screening room in the Clinical Neuromodulation Laboratory space in [name] research suite. Informed consent will be reviewed with the potential participant by a member of the key personnel on this proposal. The consent will be signed by the participant as well as one of the Key Personnel on the proposal. A copy of the consent will be given to the subject and the original placed in the research record. All records will be stored in locked departmental files. Section 301(d) of the Public Health Service Act of November 4, 1988 also protects a layer of protection for the privacy of health information for individuals that engage in federally funded medical research.

Confidentiality and Privacy

Confidentiality will be protected by collecting only information needed to assess study outcomes, minimizing to the fullest extent possible the collection of any information that could directly identify subjects, and maintaining all study information in a secure manner. To help ensure subject privacy and confidentiality, only a unique study identifier will appear on the data collection form. Any collected patient identifying information corresponding to the unique study identifier will be maintained on a linkage file, stored separately from the data. The linkage file will be kept secure, with access limited to designated study personnel. Following data collection subject identifying information will be destroyed three years after closure of the study, consistent with data validation and study design, producing an anonymous analytical data set. Data access will be limited to study staff. Data and records will be kept locked and secured, with any computer data password protected. No reference to any individual participant will appear in reports, presentations, or publications that may arise from the study.

Data and Safety Monitoring

The principal investigator will be responsible for the overall monitoring of the data and safety of study participants. The principal investigator will be assisted by other members of the study staff.

Data and Safety Monitoring

The principal investigator (PI) will be the primary party responsible for data management, oversight, and accountability in terms of participant safety and consent. Quality control will include regular data verification (Integrity of the Consent and HIPAA, scores on assessments), study progress, subject status, adverse events, and protocol deviations. Protocol adherence will be monitored by the Wake Forest IRB, who will also be given access to the reports from the PI to the ME.

Plans for Interim Analysis of Efficacy Data: Data from this study will be analyzed when a 50% recruitment goal is obtained. Final analysis will occur when all TMS visits have been completed.

Responsibility for Data and Safety Monitoring: The PI and protocol-approved research team are all responsible for data and safety monitoring. The PI will be most involved in data and safety oversight. The PI will discuss data integrity and inquire about safety/patient tolerance in weekly meetings with the research team.

Data Entry Methods: Data will be collected using REDCap™, which is a secure web application for building and managing online surveys and databases. REDcap™ supports online or offline data capture for research studies and operations. Participants and protocol-approved study personnel will enter data directly into the online portal to ensure security and prevent data loss.

Data Analysis Plan: Data for this study (behavioral assessments) will be acquired by protocol-approved members of the research team, including graduate students and research specialists. These individuals will also perform data management and analysis under the guidance of the PI. Manuscript composition will be led by the PI and Co-Is, with the assistance of the research team.

Quality Assurance Plan: Weekly meetings will be held between the PIs and research team to discuss any data-related problems as well as qualitative comments received during data collection. Initial data analyses will examine distributions of variable scores, and comparability of baseline characteristics across conditions, any necessary adjustments to analyses will be made. Confidentiality protections are outlined below.

Statistical review of the study will be conducted annually by a Wake Forest biostatistician (including enrollment, retention, assessment inventories).

Definition and Reporting of AEs/SAEs to the IRB/NIH: An adverse event (AE) is defined as any untoward medical occurrence in a study subject who was administered rTMS but does not necessarily have a causal relationship with this treatment. Any unwanted change, physically, psychologically or behaviorally, that occurs in a study participant during the course of the trial is an adverse event. A Serious Adverse Event (SAE) is defined as an adverse event that has one of the following outcomes: death, life-threatening, inpatient hospitalization or prolongation of existing hospitalization, persistent or significant disability/incapacity, a congenital anomaly/birth defect.

All unexpected AEs will be reported to the Wake Forest Institutional Review Board (IRB) and Committee on Human Research within 48-business hours. Serious AEs will also be reported within 24-business hours. Follow-up of all unexpected and serious AEs will also be reported to these agencies. AEs/SAEs are documented and reported as per IRB requirements. Research staff will identify AEs and obtain all available information to assess severity, seriousness, study relatedness, expectedness, outcome, and the need for change or discontinuation in the study intervention. AEs are documented on AE Logs and AE Case Report Forms. Additional relevant AE information, if available, will be documented in a progress note and stored in the research record as appropriate to allow monitoring and further evaluation. If the AE meets the definition for serious, appropriate SAE protocol specific reporting forms are completed and disseminated to the appropriate persons and within the designated timeframes as indicated above. For each AE/SAE recorded, the research staff will follow the AE/SAE until resolution, stabilization, or until the participant is no longer in the study as stated in the protocol. We will report adverse events to the Medical Wake Forest IRB online per the IRB's guidelines.

Collection and Reporting of AEs and SAEs: As mentioned above, all AEs/SAEs are documented and reported as per IRB requirements. Research staff will identify AEs, verify event with the participant, and

obtain all available information to assess severity, seriousness, study relatedness, expectedness, outcome, and the need for change or discontinuation in the study intervention. AEs are documented on AE Logs and AE Case Report Forms. Additional relevant AE information, if available, will be documented in a progress note and stored in the research record as appropriate to allow monitoring and further evaluation. If the AE meets the definition for serious, appropriate SAE protocol specific reporting forms are completed and disseminated to the appropriate persons and within the designated timeframes as indicated above. If applicable, copies of medical records and injury reports will be retrieved and safely stored in the subjects file. De-identified copies of reports will be sent to the Wake Forest IRB and ME/DSBM. For each AE/SAE recorded, the research staff will follow the AE/SAE until resolution, stabilization, or until the participant is no longer in the study as stated in the protocol.

Reporting of Unanticipated Problems, Adverse Events or Deviations: Any unanticipated problems, serious, and/or unexpected AEs, deviations or protocol changes will be reported within 24-72 business hours, depending on severity, by the principal investigator or designated member of the research team to the Wake Forest IRB, ME/DSMB and to the sponsor, NIH.

Management of SAEs or Other Study Risks: As described above, SAEs will be immediately reported, within 24 business hours, to the ME/DSBM, sponsor and Wake Forest IRB. For each SAE recorded, the research staff will follow the SAE until resolution, stabilization, or until the participant is no longer in the study as stated in the protocol. If applicable, copies of medical records and injury reports will be retrieved and safely stored in the subjects file. De-identified copies of reports will be sent to the Wake Forest IRB, ME/DSBM, and NIH.

Reporting of IRB Actions and ME/DSMB Reports to NIH: Any IRB actions and ME/DSMB reports will be reported to both the Wake Forest IRB and the NIH Institute supporting the study following the sponsor's report submission guidelines, should this study be awarded.

Report of Changes or Amendments to the Protocol: Any changes to the proposal/protocol must be approved by the NIH Institute supporting the study. Any amendments to the IRB protocol associated with the proposed work will be reported to NIH should this proposal be awarded funding.

Trial Stopping Rules: The protocol will immediately be paused following notification of a SAE. Per IRB policy, the IRB and ME/DSMB will be notified within 24 business hours following the SAE notification. SAEs will be reported to NIH within 72 hours. Should the reported SAE be confirmed as directly related to the protocol, the trial will be terminated. The device manufacturer will be notified within 72 business hours. Of note, according to the literature associated with the MagVenture device, there have been no clinical trials stopped or SAEs reported.

Conflict of Interest: Neither the PI, nor members of the research team have any Conflicts of Interest directly related to this protocol. The rTMS device used for the proposed study is manufactured by MagVenture.

Reporting of Unanticipated Problems, Adverse Events or Deviations

Any unanticipated problems, serious and unexpected adverse events, deviations or protocol changes will be promptly reported by the principal investigator or designated member of the research team to the IRB.

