Official Title: The Effect of Dorsolateral Prefrontal Cortex Theta Burst Stimulation on Alcohol Cue Reactivity and Cognitive Control: a Double-blind, Sham Controlled Study of Heavy Alcohol Drinkers With a History of Alcohol Related Injury.

NCT04223154

IRB-Approved Date: 8/25/20

Study Title: The effect of dorsolateral prefrontal cortex theta burst stimulation on alcohol cue reactivity and cognitive control: a double-blind, sham controlled study of heavy alcohol drinkers with a history of alcohol related injury.

Principal Investigator, Co-investigator(s): [name]; [name]

Sponsor or funding source: Internal

Background, Rationale and Context

Background: Theta Burst Stimulation (TBS) is a patterned form of repetitive transcranial magnetic stimulation – a non-invasive technique which uses electromagnetic induction to discharge populations of neurons in the vicinity of the induced electrical field. Although the exact electrophysiologic mechanism of TBS is not understood on a cellular level, the induced E-field is strong enough to reliably result in motor evoked potentials in a somatotopic manner. The focality of stimulation is related to the shape of the coil, wherein a typical figure-of-8 coil (as used in the proposed pilot project) affects approximately 10cm² of cortical surface and has a 1-2cm² penetration depth (Deng et al 2010). When this depolarizing current is strong enough however, it is possible to induce activity in monosynaptic targets of the neurons directly affected by the field. In this manner, cortical pulses of TMS can be used to investigate frontal-striatal connectivity. Although the effects of TBS on dopamine binding have not yet been assessed [Note: a project the PI would also like to do at Wake Forest in the near future], traditional fixed frequency 10Hz stimulation to the left dLPFC appears to increase dopamine binding in the caudate (Strafella et al 2001), and dorsal medial PFC TMS increases dopamine binding in the cingulate and orbitofrontal cortex (Cho et al 2005). In the first sham-controlled evaluation of single pulse TMS in the MRI scanner, we recently demonstrated that TMS pulses lead to a causal increase in BOLD signal specific to the caudate and the anterior cingulate cortex (Dowdle et al 2019).

[figure not shown]

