Hence, the goal of this proposal is to evaluate **Strategy 2 of the CNDS theory- increasing activity in executive control circuitry- as an innovative approach to dampening alcohol cue-reactivity (Aim 1) and improving cognitive control in the presence of an alcohol cue (Aim 2)**. This will be achieved through a double-blind, sham-controlled cohort study in 48 heavy alcohol drinkers with a history of alcohol-related injury. The brain reactivity to alcohol cues (Incentive Salience) and cognitive performance in the presence of an alcoholic beverage cue (Cognitive Control) will be measured immediately before and after participants receive real or sham intermittent theta burst stimulation (iTBS- a potentiating form of transcranial magnetic stimulation) to the dorsolateral prefrontal cortex (dLPFC iTBS). iTBS is a high-potency form of brain stimulation wherein two minutes of iTBS (600 pulses) leads to an increase in cortical excitability that lasts for approximately 30 minutes (Huang et al. 2005). In 2018, dLPFC iTBS was FDA-cleared as a treatment for major depressive disorder (wherein 30 sessions over 6 weeks lead to a sustained decrease in depressive symptoms for 6 months; Blumberger et al. 2018). In 2019, the first 2 manuscripts were published demonstrating that iTBS decreases cue-reactivity to cocaine (Steele et al 2019, Sanna et al 2019). **The goals of this pilot study are to quantify the acute effect of a single session of real or sham dLPFC iTBS on brain response to alcohol cues (Aim 1) and cognitive flexibility in the presence of an alcohol cue (Aim 2) among risky drinkers (“target engagement”)**.

Aim 1: Evaluate the effect of dLPFC iTBS on alcohol cue-reactivity. The blood-oxygen level dependent (BOLD) signal associated with exposure to alcohol cues will be measured before and after sham and real iTBS using a validated, patient-tailored alcohol/non-alcoholic beverage cue task. Hypothesis: cue-evoked functional connectivity in the dLPFC, ACC, amygdala, and ventral striatum will be attenuated after real but not sham iTBS.

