Aim 2: Evaluate the effect of dLPFC iTBS on cognitive performance in the presence of an alcohol cue. Following the alcohol cue reactivity task all individuals will perform the well-known alcohol Stroop task (downloaded from the NIH toolbox) on a Tablet PC while a glass of the participant’s preferred alcoholic beverage (beer, wine, liquor) is placed within 5 feet of the participant (but out of arms length). This will occur before and after TBS. The participant will not be allowed to consume the drink. Hypothesis: Stroop accuracy and reaction time will be impaired at baseline, but this difference will be attenuated by real (but not sham) iTBS to the dLPFC (three way mixed model ANOVA, correcting for multiple comparisons).

Methods and Measures

Design

Our primary goal is to determine the extent to which one session of dLPFC iTBS can attenuate limbic circuitry involved in alcohol cue-reactivity (Aim 1) and cognitive control in the presence of an alcohol cue (Aim 2) among heavy alcohol users with a history of risky drinking behavior. This will be tested in a cohort of 48 heavy alcohol users, recruited through the resources of the Wake Forest Trauma Unit Registry and from the community at large through advertisements. This double-blind, sham-controlled study will involve 1 Screening visit and 1 TBS/MRI Scanning Visits. At the scanning/stimulation visit, functional MRI data will be collected before and after exposure to a session of real or sham theta burst stimulation (Figure 1). TBS will be applied over the left dorsolateral prefrontal cortex (landmark based on EEG 10-20 system: F3). A series of clinical assessments of drinking behavior and other relevant psychosocial and demographic measurements will also be collected (Table 1). We will test the hypotheses that TBS over the dLPFC will attenuate the neural response to alcohol cues (Aim 1) and improve cognitive performance in the presence of an alcoholic beverage cue (Aim 2). The results of these aims will be further evaluated in terms of their relationship to alcohol drinking severity and demographic factors. These data will be preliminary data for a subsequent R01 focused on the sustained effects

of multiple sessions of TBS as a tool to decrease drinking among individuals with AUD and lowering morbidity and hospital recidivism among these patients.

Setting

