Interdisciplinary Research Team: The Principal Investigator, [name] is a professor in the Department of Cancer Biology leading a new human brain stimulation research group at Wake Forest. She has expertise in neuroscience, human neuroimaging and brain stimulation in substance dependent individuals. [name] is an associate professor in the Department of Surgery wherein she leads a comprehensive screening and brief intervention research program designed to identify and decrease alcohol use among individuals that present to the Inpatient Trauma Unit.

All study activities will take place at Wake Forest University of Health Sciences.

[name] primary office and research laboratory is located in the Clinical Neuromodulation Laboratory in the Department of Cancer Biology at Biotech Place. [name] lab space will include a room dedicated for all research related activities including a space for screening participants and a space dedicated for TMS stimulation.

The majority of the contents of this study, however, will take place at the MRI center located on [name] on the main campus of Wake Forest Baptist Health. This will utilize the 3T scanner in the MRI center and will have an outfitted setup including a laptop computer and desk for participant interviewing, as well as a TMS device.

Finally, recruitment efforts will come from associated clinics at Wake Forest University of Health Sciences, including the Department of Psychiatry and the Inpatient Trauma Unit. Collaborative efforts will be maximized in order to recruit subjects from the associated Wake Forest University Trauma Unit Registry and from the community at large.

In response to COVID-19: During COVID-19, interactions with study subjects will take place through videoconferencing. Prior to any remote consent/screening videoconference visit, the participant will be sent a copy of the ICF via mail/email to sign while the virtual meeting is taking place. Once this is signed, the participant will mail/email this back to the study staff to sign before proceeding with any research related activities.

Subjects selection criteria

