Forty eight heavy alcohol users between 21 and 70 years old will be recruited through the resources of the Trauma Registry and the Piedmont Triad area. Participants will be prescreened by phone for eligibility. Potentially eligible participants will be invited for an in-person screening visit where, after signing informed consent they will receive a detailed evaluation and urine toxicology screen for illicit drugs. Individuals that remain eligible will then undergo the Stimulation/Scanning (see below).

Inclusion Criteria

1. Ages 21-70.
2. Alcohol use disorder identification test (AUDIT) score >7 or a clinician-determined risk score of Moderate to Severe on the Screening, Brief Intervention, and Referral to Treatment (SBIRT).
3. Drink at least 15 standard sized alcohol beverage servings per week sometime in the past month or have had a blood alcohol level of 140+ on admission to the trauma unit following injury.

Exclusion Criteria

1. Current use of prescription or illicit psychoactive drugs (except marijuana or nicotine) known to decrease seizure threshold by self-report in the last 30 days.
2. Currently meets DSM-V criteria for substance use disorder for a substance other than alcohol, marijuana, or nicotine.
3. Has current suicidal or homicidal ideation.
4. Not currently in or at risk for withdrawal, as indicated by CIWA-Ar >5.
5. History of seizures and/or seizure disorder(s).
6. Females of childbearing potential who are pregnant (by urine HCG), planning to become pregnant, nursing, or who are not using a reliable form of birth control.
7. Any other violation of MRI/TMS safety measures.
8. Unable to read and understand questionnaires, assessments, and the informed consent.
9. No presence of metal objects in the head/neck.
10. History of traumatic brain injury resulting in hospitalization, loss of consciousness for more than 10 minutes, and/or having ever been informed he/she has an epidural, subdural, or subarachnoid hemorrhage.

Sample Size

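### The title and cohort sentence claim a past alcohol-related injury that the inclusion criteria do not require; separately, exclusions 4 and 9 are worded in the negative and literally exclude the opposite group

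*Combined protocol and SAP*

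**What the plan says.** **Stated population.** The official title announces a "Sham Controlled Study of Heavy Alcohol Drinkers With a History of Alcohol Related Injury". The Objectives repeat this as a "double-blind, sham-controlled cohort study in 48 heavy alcohol drinkers with a history of alcohol-related injury". A later sentence in the Objectives says only "among risky drinkers". The Design section, in its primary-goal sentence, and Subject Recruitment Methods describe heavy users with past risky drinking and do not mention injury as a requirement.

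**Inclusion criteria.** Item 1 is age 21 to 70. Item 2 is "Alcohol use disorder identification test (AUDIT) score >7 or a clinician-determined risk score of Moderate to Severe" on the SBIRT. Item 3 begins "Drink at least 15 standard sized alcohol beverage servings per week sometime in the past month or have had a blood alcohol level of"; its second alternative in full is a "blood alcohol level of 140+ on admission to the trauma unit following injury".

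**Recruitment.** Under Design, participants are to be "recruited through the resources of the Wake Forest Trauma Unit Registry and from the community at large through advertisements". The Setting section likewise plans to "recruit subjects from the associated Wake Forest University Trauma Unit Registry and from the community at large". Subjects selection criteria and Subject Recruitment Methods also go beyond trauma sources.

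**Exclusion criteria.** Item 4 lists not being in, or at risk of, withdrawal, and gives a CIWA-Ar score above 5 as the indicator. Item 9 lists the absence of metal in the head or neck. Risks Associated with MRI Scanning says that people with metallic implants are excluded. The entry on electrical or metal implants under Other potential risks excludes people who have such implants or suspect metal in the eyes, head or body, and provides for a TMS safety questionnaire.

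**The concern.** **Population.** A reader of the title will take the results to be about drinkers who have been injured through drinking. If part of the sample has no such history, that description is wrong for those participants. This matters beyond labelling style because the Objectives name Trauma Unit patients with alcohol use disorder as the long-term target, and the Design section presents the trial as preliminary data for a larger grant application. Without a count of injury history, nobody can say how far the results describe the titled population.

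**Exclusions.** Items 4 and 9 are operative, safety-related eligibility rules. A screening form that took its wording from the list would carry the inverted sense. Item 9 has other text to set against it. Item 4 does not.

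**Working it through.** The plan gives no figure to reproduce here. The check compares passages.

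**Step 1: does any inclusion criterion make injury necessary?** Item 1 (age) and item 2 (risk score) contain no injury element. Item 3 joins two alternatives with *or*:

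| 15+ servings per week | Blood alcohol 140+ on trauma admission | Item 3 | Injury established by the criterion |
|---|---|---|---|
| no | no | not met | no |
| no | yes | met | yes |
| yes | no | met | no |
| yes | yes | met | yes |

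The third row is the gap. A community volunteer aged 21 to 70 with an AUDIT score above 7 who drinks 15 servings a week meets every inclusion criterion without any injury. A *no* in the last column means that injury is not required, not that it is absent.

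**Step 2: is that route meant to be used?** Yes. Design, Setting, Subjects selection criteria and Subject Recruitment Methods all look beyond trauma sources, and no minimum number from those sources is set.

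**Step 3: which text is out of line?** The criteria, the recruitment text and the Design section's description of past risky drinking agree with one another. The title and the cohort sentence do not agree with them.

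**Step 4: how large is the effect?** The documents give no expected split between trauma and community sources, and no rate of past injury among community drinkers. The share entering without an injury therefore cannot be computed.

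**Step 5: exclusions.** Of 10 exclusions, items 4, 6, 8 and 9 contain a negative. Items 6 (no reliable contraception) and 8 (unable to read the materials) work as exclusions. Items 4 and 9 do not: 2 of 10 are inverted.

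- *Item 9.* Taken literally, it excludes people without head or neck metal. The implant entry excludes people with metal in the eyes, head or body. Applied together, the two rules leave nobody eligible, so they contradict each other. The body regions also differ (head and neck against eyes, head or body), and removing the negative would not resolve that.
- *Item 4.* Taken literally, it excludes people who are not in or at risk of withdrawal. Its own clause offers a score above a cut-off as the indicator, which fits a condition being present better than one being absent. This assumes that higher scores mean more withdrawal; the documents do not define the scale. No other section mentions CIWA-Ar or alcohol withdrawal.

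**The case against.** **The operative text is already consistent.** The Design section, the recruitment text and the criteria agree on past risky drinking, so the mismatch is confined to the title and one sentence. This stands, and it makes the population issue a correction of description. It does not remove the issue, because the title and the cohort sentence are what readers will carry into the conclusions.

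**The blood-alcohol route.** A reader might infer that no entry route guarantees both heavy drinking and injury, because the blood-alcohol alternative sets no weekly quantity. The documents do not support this. They never define heavy use as a weekly amount, and the criteria can themselves be read as the working definition.

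**The possible range.** A reader might also infer that anything from none to all 48 could lack an injury. With no quota the criteria allow it, but a range that covers every possible outcome is not an estimate. Its upper end also sits poorly with the planned recruitment from the Trauma Registry and the inpatient unit.

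**Staff will know what items 4 and 9 mean.** The literal reading is unworkable, and the score clause in item 4 signals a slip. Both points are fair, and it would go too far to infer that people in withdrawal will be enrolled or that item 4 is beyond interpretation. No inverted screening form appears in the documents either. Item 7, the general clause on MRI and TMS safety, supports item 9. It is a weak backstop for item 4, because no section lists withdrawal among those safety measures. An eligibility rule should still say what it means.

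**The data may already be collected.** Visit 1 includes past medical history, and Table 1 is not in the available text. The request to record injury history is therefore conditional.

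**Conclusion.** Both parts hold.

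**Population.** The title and the cohort sentence claim an injury history that the criteria require in only one of the two alternatives of inclusion 3. Conclusions about drinkers with alcohol-related injury would not hold for the whole sample. The size of the discrepancy is unknown and cannot be derived from the documents. A reader might infer bias in the real-versus-sham comparison, but the documents give no ground for that: both arms are randomised from the same eligible population.

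**Exclusions.** Two of the 10 items are inverted as written. Item 9 contradicts the risk sections and differs from the implant entry in the body regions covered. Item 4 is the only withdrawal rule. Its internal wording points to a drafting slip, but no other passage confirms the intended sense.

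These are certain, inexpensive corrections to the population for inference and to two safety-related rules. They do not undermine the trial's design.

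**What to change.** **Population.** The sponsor should make the two descriptions agree, in one of two ways:

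- Keep the criteria and recruitment, and reword the title, the cohort sentence and any conclusions to describe the people the criteria admit, with or without an alcohol-related injury.
- If the title population is intended, bring the inclusion criteria and the recruitment text into line with it.

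In either case, report the number with and without an alcohol-related injury history in each arm, descriptively only. Record it at Visit 1 if it is not already collected; for those entering through the blood-alcohol alternative, injury is established at entry.

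**Exclusions.** The sponsor and investigator must reconcile the wording of items 4 and 9 with their intended sense and with the two risk sections, including the body regions covered, and correct the protocol and any screening form derived from it. No clinical rule is proposed here.

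**Cost.** A wording amendment through the IRB, plus at most one history item. The title page lists funding as internal, so the NIH approval and reporting steps under Report of Changes or Amendments to the Protocol matter only if an NIH award applies. Keeping the criteria and correcting the two exclusions leaves sample size and analysis unchanged. Narrowing to the title population would mean rechecking the forecast of 3 to 4 participants per month, on which the 12 to 16 months of recruitment rest (48/4 = 12; 48/3 = 16).
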